8.2.3.1 Pharmacokinetics

Individual values will be listed for the PK parameters as shown below, and the following (non-model-based) descriptive statistics will also be provided: N (number of subjects with non-missing data), arithmetic mean, standard deviation, arithmetic percent CV (calculated as $100 \times$ standard deviation/arithmetic mean), median, minimum, maximum, geometric mean, and geometric percent CV (calculated as $100 \times \sqrt{\exp(s^2)} - 1$, where s^2 is the observed variance on the natural log-scale). On Day 10, the PK parameters are steady-state C_{avg} , AUC_{0-24hr} , C_{max} , C_{min} and T_{max} in subgroup 1. The frequency distribution with pre-specified exposure in two categories, <500 ng/mL and ≥ 500 ng/mL, for steady-state C_{avg} values on Day 10 in subgroup 1 will be tabulated. Descriptive statistics (mean and arithmetic percent

CV) will also be tabulated for trough plasma concentrations in both subgroups by study day for MK-5592. In addition, mean trough plasma concentrations in both subgroups will be plotted by study day.

A population PK model was developed in non-Chinese healthy volunteers and patients to characterize PK and its variability after POS IV administration. Data from this study will be added to the dataset and the effect of Chinese ethnicity on the pharmacokinetics of posaconazole will be assessed. Also the percentage of the population with $C_{avg} \geq 500$ ng/mL will be estimated using the population PK model. Other necessary pharmacokinetic parameters will also be estimated from the population PK models.

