2.2 Trial Diagram

This is an open-label, single arm, multi-center study with two sub-groups. At least 3 investigative sites in China will be selected for this study.

Subjects will be allocated to one treatment group with same treatment regimen; while there will be 2 subgroups for different pharmacokinetic sampling schemes as indicated below ([Figure 1](#), Trial Design). Approximately 30 subjects will be allocated to subgroup 1, and about 40 subjects will be allocated to subgroup 2. The two subgroups will receive same treatment but different blood sample collection schemes in order to characterize the pharmacokinetics in the whole study population.

After a screening phase of 14 days, each subject will receive POS intravenous (IV) solution 300 mg Q12h on Day 1, followed by 300 mg QD on Day 2 through 10 (± 1) via central line administration. Then, subjects will receive IV solution 300 mg QD or oral suspension (OS) 200 mg TID for up to 18 (± 1) days at the discretion of investigator. The investigator could switch the subject back to POS IV solution treatment during oral treatment period if the subject is unable to tolerate oral suspension. The total treatment duration is at least 10 (± 1) days to up to 28 days. After the end of treatment (EOT), each subject will be followed for 30 days for safety. A survival assessment will be performed on any day from Days 60 to 70.

The trial design is depicted in [Figure 1](#).

- For subgroup 1, blood samples for plasma trough POS levels will be drawn on Days 3, 6, 10 (± 1), 15 (± 1), 22 (± 1), and 28/EOT. Additional PK samples will be drawn on Day 10 (± 1) at pre-dose, 1 hour post start of infusion, immediately before the end of infusion, approximately 15 minutes after the end of infusion, and approximately 4, 8, 12 and 24 hours post start of infusion. The intensive PK for POS IV solution on Day 10 (± 1) must be obtained before switching to oral suspension.
- For subgroup 2, blood samples for plasma trough POS levels will be drawn on Days 3, 6, 10 (± 1), 15 (± 1), 22 (± 1), and 28/EOT.

Figure 1 Study Design

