5.2.1 Dose Selection/Modification

5.2.1.1 Dose Selection (Preparation)

The proposed dosing regimen of POS IV solution for the prophylaxis of invasive fungal infections is a loading dose of 300 mg Q12h on the first day, then 300 mg QD thereafter. Subject could be switched to oral suspension as 200 mg TID based on the judgment of physicians after the intensive PK samplings are completed on Day 10 (± 1 day).

The rationale for selection of doses to be used in this trial is provided in Section 4.0 – Background & Rationale. There are no specific calculations or evaluations required to be performed in order to administer the proper dose to each subject.

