5.2.2 Timing of Dose Administration

MK-5592 IV solution will be administrated through central line for approximately 90 minutes, the residual volume, if any, should be documented. Subjects will have their IV infusions began at approximately the same time each day. The first three IV infusions must be given not less than 10 hours or no more than 14 hours apart. The subsequent IV infusions must be given not less than 22 hours or no more than 26 hours apart, in order to control one source of variability in drug levels. MK-5592 IV solution will be dosing without regard to food intake.

If the dosing of MK-5592 IV solution for the other days besides the day 1 is delayed, the dose of MK-5592 IV solution for the remaining days of the study should be taken following completion of the trough PK blood sampling (see flow chart for applicable study days) with at least 8 hours separating the prior day's dosing. Every attempt should be made to ensure that the subject given study medication once daily following the Q12h dosing on Day 1.

If the treatment of the subject switches to POS oral suspension at the discretion of investigator from Day 11 (± 1) to Day 28 or EOT, which occurs first. For subjects in subgroup 1, the intensive PK for POS IV solution must be obtained before switching to oral suspension. The oral suspension should be given under the guidance of physicians per local label. The POS oral suspension should be administered with food or immediately after eating (i.e., within 20 minutes). The investigator may switch the subject back to POS IV solution if the subject is unable to dose with food or tolerate oral medication. Subjects who vomit within 30 minutes of POS oral administration should be given a single replacement dose as soon as possible or per guidance of the physician, following appropriate antiemetic treatment.

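### Trough tables and plot by study day do not separate IV from oral-suspension samples, so the late-day values can mix two formulations in an unplanned proportion

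*Combined protocol and SAP*

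**What the plan says.** The trough display is specified in 8.2.3.1 and in the same words in 8.1. Mean and arithmetic CV "will also be tabulated for trough plasma concentrations in both subgroups by study day for MK-5592", and "mean trough plasma concentrations in both subgroups will be plotted by study day". The only classifiers are study day and PK subgroup.

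Troughs are drawn in both subgroups on Days 3, 6, 10 (±1), 15 (±1), 22 (±1) and 28/EOT. After the IV phase, section 2.2 states that "subjects will receive IV solution 300 mg QD or oral suspension (OS) 200 mg TID", the choice being left to the investigator. Section 5.2.2 adds that "The investigator may switch the subject back to POS IV solution". No section sets or predicts the share of subjects who will switch.

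PK subgroup cannot stand in for formulation, because section 2.2 says "The two subgroups will receive same treatment but different blood sample collection schemes".

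The stated interest is the IV solution. Section 3.1 names it in the primary objective, 4.2.3.1 defines Cmin as the level before an IV dose, and 8.2.2 ties the named parameters to IV administration.

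**The concern.** A programmer following 8.2.3.1 literally would produce one row per day and subgroup. On Days 15, 22 and 28/EOT that row can combine subjects on once-daily IV with subjects on three-times-daily suspension. Section 4.1.1 says the IV formulation was developed for higher and less variable exposure than the suspension. Mean and CV, the two statistics planned for this table, are therefore the two that the sponsor expects to differ by formulation.

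This is the only planned descriptive display of exposure after Day 10. If the mean drifts down or the CV widens on the late days, a reader could not tell whether IV exposure changed or whether more subjects had moved to suspension. The flow chart's trough definition, about 24 hours after the previous day's dose, also fits once-daily dosing and not three-times-daily dosing.

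**Working it through.** **Which samples are exposed**

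- Days 3 and 6: IV only. Not affected.
- Subgroup 1, Day 10 (±1): protected. Section 5.2.2 states that "For subjects in subgroup 1, the intensive PK for POS IV solution must be obtained before switching to oral suspension". The Day 10 Cavg, AUC and ≥500 ng/mL results are protected for the same reason.
- Subgroup 2, Day 10 (±1): possibly affected. The rule just quoted names subgroup 1 only. Section 5.2.1.1 allows switching "after the intensive PK samplings are completed on Day 10", but subgroup 2 has no intensive sampling. A subject "switches to POS oral suspension at the discretion of investigator from Day 11" (±1), so oral dosing may start on Day 10, while the trough window runs to Day 11.
- Days 15, 22 and 28/EOT, both subgroups: affected if anyone has switched.

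**Inputs**

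- IV Cavg 1500 ng/mL, CV 35% (8.2.3.3). As a check on these inputs, a normal distribution with SD 525 gives P(Cavg ≥ 500) = 0.972. The chance of at least 18 of 20 is then 0.982, which agrees with the plan's figure of more than 90%. That calculation is not in dispute.
- Oral suspension 200 mg TID (12.10, Table 11): Cavg 583 ng/mL, CV 65% in AML/MDS, the closer population; or 1103 ng/mL, CV 67% in HSCT with GVHD.
- Half-life about 30 h (4.2.2.1).
- Assumed: share switched w = 25, 50 or 75%. Cavg CVs are carried over to troughs.

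**Cavg to trough** (one compartment, bolus input, k = ln 2/30 per h)

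Trough/Cavg = kτ·exp(−kτ)/(1 − exp(−kτ)), which is 0.748 for τ = 24 h and 0.910 for τ = 8 h.

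- IV: 1500 × 0.748 = 1122 ng/mL
- Oral: 583 × 0.910 = 531, or 1103 × 0.910 = 1004 ng/mL

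**Pooled row** (I = IV trough, O = oral trough)

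Mean = (1 − w)I + wO. Variance = (1 − w)(0.35·I)² + w(CV_O·O)² + w(1 − w)(I − O)².

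| Share switched | Mean, O = 531 | CV | Mean, O = 1004 | CV |
|---|---|---|---|---|
| 25% | 974 (13% below IV) | 47% | 1093 (3% below) | 44% |
| 50% | 827 (26% below) | 57% | 1063 (5% below) | 52% |
| 75% | 679 (40% below) | 65% | 1034 (8% below) | 60% |

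The IV-only row would be 1122 ng/mL with CV 35% in every case.

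**Sensitivity at 50% switched** (change in mean for the 583 and 1103 figures)

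- Cavg used directly as trough: 31% and 13% below. This overstates the effect.
- Flat oral profile: 24% and 1% below.
- IV trough/Cavg ratio of 0.66, inferred from the 99.7% and 93.6% above 500 ng/mL in 4.1.1 with log-SD 0.340: exp(−(2.748 − 1.522) × 0.340) = 0.66. This gives 23% below and 1% above.

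**Carry-over after a switch,** 0.5^(t/30)

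- Subgroup 2, switched on Day 10 and sampled on Day 11: 0.574 of the IV–oral difference remains. That subject's expected trough is 531 + 591.6 × 0.574 = 870 ng/mL (22% below IV), or 1072 ng/mL (4% below) with the 1103 figure.
- Day 15 after a Day 11 switch: 0.109 remains. The pooled mean at 50% switched is 859 ng/mL (23.5% below) or 1070 ng/mL (4.7% below). Carry-over reduces the effect only slightly.

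**The case against.** The strongest reply is that this is silence about a table layout and that the text leans towards separation. Section 8.2.3 says data are analysed by treatment received, Table 2 lists the IV solution and the suspension on separate rows, and Cmin is defined for IV. These sentences show what the sponsor cares about but do not govern this display. The as-treated sentence names no formulation, and section 1.0 describes a single treatment regimen. The IV wording in 8.2.2 covers the named parameters, while the trough-by-day summary has its own sentence without that limit.

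A second reply is that mean trough under the whole sequential regimen is a legitimate quantity. It is, but it is not IV exposure, and the plan does not label it as regimen-level exposure. It is also true that a late IV-only group is selected by the investigator's choice. The fix must say so.

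Third, the subgroup 2 Day 10 case needs the ±1 windows to combine, and a single shared shift is a natural reading. That is fair, and the case is offered only as a possibility.

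Fourth, the magnitude rests on assumptions. This stands. With the 1103 figure the shift in the mean is small and its sign is not settled. At 50% switched, the three variance terms are about 77,200, 226,300 and 3,500, so the wider CV there comes almost wholly from the historical oral CV of 67%. The 583 figure may overstate the drop, since the protocol recommends high-fat meals and lets subjects who cannot dose with food return to IV. The AUC in the same table row implies 15,900/24 = 662 ng/mL. The 0.66 ratio is also rough: a lognormal with mean 1500 and CV 35% puts about 99.9% above 500, not 99.7%.

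Finally, the population PK model will use all the data, and formulation can be recovered later from dosing records. Both are true, and both limit the consequence. Neither makes the planned table and plot readable.

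**Conclusion.** The concern holds, as a minor one. As written, the Day 15, 22 and 28/EOT trough summaries can mix two formulations in a proportion nobody has planned, and subgroup 2's Day 10 (±1) value may be affected too. Confidence is high on the gap in the text. The size is uncertain because the documents give neither the switched share nor trough means and CVs, and because historical oral figures may not carry over to subjects chosen for switching. Under the stated assumptions, with 25 to 75% switched, the pooled mean is 13 to 40% below IV with the AML/MDS figure and 3 to 8% below with the HSCT/GVHD figure. Pooled CV is 44 to 65% instead of 35%. No primary result, test, decision rule or sample size depends on this display.

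**What to change.** In 8.1 and 8.2.3.1:

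- Classify every trough from Day 10 (±1) onward by formulation at sampling, using dosing records and the medication diary.
- Tabulate and plot by study day and formulation, with N in each cell. Pool the two PK subgroups where cells are small, since they receive the same treatment.
- Base the IV trough summary on subjects who have received only IV up to that sample. List or flag those who returned to IV.
- State that the late IV-only group is selected by investigator discretion and is not a neutral estimate of late IV exposure.

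The cost is SAP wording and one derived variable. No new procedures are needed, and nothing changes in who switches or when. The downside is smaller cells. If subgroup 1's 30% dropout applied to everyone, 70 × 0.7 = 49 subjects would be evaluable. With 25/50/75% switched, about 37/24/12 IV-only subjects per day would remain with subgroups pooled. Split by subgroup at 50%, there would be about 10 (21 × 0.5) and 14 (28 × 0.5) per formulation, and fewer on the later days.

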8.2.3.2 Safety

Safety will be evaluated in Chinese subjects by clinical assessment of adverse experiences and other safety parameters. Adverse experience will be listed and tabulated. Summary statistics for the raw laboratory safety tests, ECGs, and/or vital signs may also be computed, as deemed clinically appropriate. Descriptive statistics will be provided for the survival assessment (any day between Days 60 and 70).

8.2.3.3 Sample Size

The sample size for this study is based on overall objectives such as PK, safety and tolerability. Assuming a mean steady-state $C_{avg} = 1500$ ng/mL and a coefficient of variation (CV) = 35%, there is a greater than 90% probability that at least 18 out of 20 evaluable subjects enrolled in subgroup 1 will have a steady-state $C_{avg} \geq 500$ ng/mL. These calculations are based on the data of steady-state pharmacokinetics from 49 subjects enrolled in an earlier study of POS IV solution (P05520, [Table 5](#)). In order to have approximately 20 evaluable subjects in subgroup 1 and considering a potential dropout rate 30%, approximately 30 subjects will be enrolled in subgroup 1. The sample size for subgroup 2 is based on prior study experience and historical requirements for filing regarding the number of subjects that would need to constitute an adequate safety database for this formulation. Therefore, we will enroll approximately 30 subjects in subgroup 1 and 40 subjects in subgroup 2.

Table 5 PK Parameters Based on Previous Studies

Endpoint	Mean	CV	Source
C_{avg}	1500 ng/ml	0.35	MK-5592 PN05520 (n=49)
C_{max}	3280 ng/ml	0.74	
T_{max}	1.5 (0.98-4.0) ^a hr	-	

^a Median (minimum-maximum).

9.0 LABELING, PACKAGING, STORAGE AND RETURN OF CLINICAL SUPPLIES

9.1 Investigational Product

The investigator shall take responsibility for and shall take all steps to maintain appropriate records and ensure appropriate supply, storage, handling, distribution and usage of investigational product in accordance with the protocol and any applicable laws and regulations.

Clinical Supplies will be provided by the Sponsor as summarized in [Table 6](#).

Table 6 Product Descriptions

Treatment Group	Product Name and Dosage Form	Dose	Potency	Total Dosage Forms	Additional Information
All (subgroup 1 and subgroup 2)	MK-5592 IV solution Or MK-5592 oral suspension	300 mg/vial for IV solution 200 mg for oral suspension	18 mg/mL for IV solution 40 mg/mL for oral suspension	1 vial for IV solution 200 mg for oral suspension	NA

9.2 Packaging and Labeling Information

Clinical supplies will be affixed with a clinical label in accordance with regulatory requirements.

9.3 Clinical Supplies Disclosure

This trial is open-label; therefore, the subject, the trial site personnel, the Sponsor and/or designee are not blinded. Treatment (name, strength or potency) is included in the label text; random code/disclosure envelopes or lists are not provided.

9.4 Storage and Handling Requirements

Clinical supplies must be stored in a secure, limited-access location under the storage conditions specified on the label.

Receipt and dispensing of trial medication must be recorded by an authorized person at the trial site.

Clinical supplies may not be used for any purpose other than that stated in the protocol.

9.5 Discard/Destruction>Returns and Reconciliation

The investigator is responsible for keeping accurate records of the clinical supplies received from the Sponsor or designee, the amount dispensed to and returned by the subjects and the amount remaining at the conclusion of the trial. For all trial sites, the local country Sponsor personnel or designee will provide appropriate documentation that must be completed for drug accountability and return, or local discard and destruction if appropriate. Where local

discard and destruction is appropriate, the investigator is responsible for ensuring that a local discard/destruction procedure is documented.

10.0 ADMINISTRATIVE AND REGULATORY DETAILS

10.1 Confidentiality

10.1.1 Confidentiality of Data

By signing this protocol, the investigator affirms to the Sponsor that information furnished to the investigator by the Sponsor will be maintained in confidence, and such information will be divulged to the institutional review board, ethics review committee (IRB/ERC) or similar or expert committee; affiliated institution and employees, only under an appropriate understanding of confidentiality with such board or committee, affiliated institution and employees. Data generated by this trial will be considered confidential by the investigator, except to the extent that it is included in a publication as provided in the Publications section of this protocol.

10.1.2 Confidentiality of Subject Records

By signing this protocol, the investigator agrees that the Sponsor (or Sponsor representative), IRB/ERC, or regulatory authority representatives may consult and/or copy trial documents in order to verify worksheet/case report form data. By signing the consent form, the subject agrees to this process. If trial documents will be photocopied during the process of verifying worksheet/case report form information, the subject will be identified by unique code only; full names/initials will be masked prior to transmission to the Sponsor.

By signing this protocol, the investigator agrees to treat all subject data used and disclosed in connection with this trial in accordance with all applicable privacy laws, rules and regulations.

10.1.3 Confidentiality of Investigator Information

By signing this protocol, the investigator recognizes that certain personal identifying information with respect to the investigator, and all subinvestigators and trial site personnel, may be used and disclosed for trial management purposes, as part of a regulatory submissions, and as required by law. This information may include:

1. name, address, telephone number and e-mail address;
2. hospital or clinic address and telephone number;
3. curriculum vitae or other summary of qualifications and credentials; and
4. other professional documentation.

Consistent with the purposes described above, this information may be transmitted to the Sponsor, and subsidiaries, affiliates and agents of the Sponsor, in your country and other countries, including countries that do not have laws protecting such information. Additionally, the investigator's name and business contact information may be included when reporting certain serious adverse events to regulatory authorities or to other

investigators. By signing this protocol, the investigator expressly consents to these uses and disclosures.

If this is a multicenter trial, in order to facilitate contact between investigators, the Sponsor may share an investigator's name and contact information with other participating investigators upon request.

10.1.4 Confidentiality of IRB/IEC Information

The Sponsor is required to record the name and address of each IRB/IEC member that reviews and approves this trial. The Sponsor is also required to document that each IRB/IEC meets regulatory and ICH GCP requirements by requesting and maintaining records of the names and qualifications of the IRB/IEC members and to make these records available for regulatory agency review upon request by those agencies.

10.2 Compliance with Financial Disclosure Requirements

Financial Disclosure requirements are outlined in the US Food and Drug Administration Regulations, Financial Disclosure by Clinical Investigators (21 CFR Part 54). It is the Sponsor's responsibility to determine, based on these regulations, whether a request for Financial Disclosure information is required. It is the investigator's/subinvestigator's responsibility to comply with any such request.

The investigator/subinvestigator(s) agree, if requested by the Sponsor in accordance with 21 CFR Part 54, to provide his/her financial interests in and/or arrangements with the Sponsor to allow for the submission of complete and accurate certification and disclosure statements. The investigator/subinvestigator(s) further agree to provide this information on a Certification/Disclosure Form, commonly known as a financial disclosure form, provided by the Sponsor or through a secure password-protected electronic portal provided by the Sponsor. The investigator/subinvestigator(s) also consent to the transmission of this information to the Sponsor in the United States for these purposes. This may involve the transmission of information to countries that do not have laws protecting personal data.

10.3 Compliance with Law, Audit and Debarment

By signing this protocol, the investigator agrees to conduct the trial in an efficient and diligent manner and in conformance with this protocol; generally accepted standards of Good Clinical Practice (e.g., International Conference on Harmonization of Technical Requirements for Registration of Pharmaceuticals for Human Use Good Clinical Practice: Consolidated Guideline and other generally accepted standards of good clinical practice); and all applicable federal, state and local laws, rules and regulations relating to the conduct of the clinical trial.

The Code of Conduct, a collection of goals and considerations that govern the ethical and scientific conduct of clinical investigations sponsored by Merck, is provided in Section 12.1 - Merck Code of Conduct for Clinical Trials.

The investigator also agrees to allow monitoring, audits, IRB/ERC review and regulatory authority inspection of trial-related documents and procedures and provide for direct access to all trial-related source data and documents.

The investigator agrees not to seek reimbursement from subjects, their insurance providers or from government programs for procedures included as part of the trial reimbursed to the investigator by the Sponsor.

The investigator shall prepare and maintain complete and accurate trial documentation in compliance with Good Clinical Practice standards and applicable federal, state and local laws, rules and regulations; and, for each subject participating in the trial, provide all data, and, upon completion or termination of the clinical trial, submit any other reports to the Sponsor as required by this protocol or as otherwise required pursuant to any agreement with the Sponsor.

Trial documentation will be promptly and fully disclosed to the Sponsor by the investigator upon request and also shall be made available at the trial site upon request for inspection, copying, review and audit at reasonable times by representatives of the Sponsor or any regulatory authorities. The investigator agrees to promptly take any reasonable steps that are requested by the Sponsor as a result of an audit to cure deficiencies in the trial documentation and worksheets/case report forms.

The investigator must maintain copies of all documentation and records relating to the conduct of the trial in compliance with all applicable legal and regulatory requirements. This documentation includes, but is not limited to, the protocol, worksheets/case report forms, advertising for subject participation, adverse event reports, subject source data, correspondence with regulatory authorities and IRBs/ERCs, consent forms, investigator's curricula vitae, monitor visit logs, laboratory reference ranges, laboratory certification or quality control procedures and laboratory director curriculum vitae. By signing this protocol, the investigator agrees that documentation shall be retained until at least 2 years after the last approval of a marketing application in an ICH region or until there are no pending or contemplated marketing applications in an ICH region or until at least 2 years have elapsed since the formal discontinuation of clinical development of the investigational product. Because the clinical development and marketing application process is variable, it is anticipated that the retention period can be up to 15 years or longer after protocol database lock. The Sponsor will determine the minimum retention period and notify the investigator when documents may be destroyed. The Sponsor will determine the minimum retention period and upon request, will provide guidance to the investigator when documents no longer need to be retained. The sponsor also recognizes that documents may need to be retained for a longer period if required by local regulatory requirements. All trial documents shall be made available if required by relevant regulatory authorities. The investigator must consult with and obtain written approval by the Sponsor prior to destroying trial and/or subject files.

ICH Good Clinical Practice guidelines recommend that the investigator inform the subject's primary physician about the subject's participation in the trial if the subject has a primary physician and if the subject agrees to the primary physician being informed.

The investigator will promptly inform the Sponsor of any regulatory authority inspection conducted for this trial.

Persons debarred from conducting or working on clinical trials by any court or regulatory authority will not be allowed to conduct or work on this Sponsor's trials. The investigator will immediately disclose in writing to the Sponsor if any person who is involved in

conducting the trial is debarred or if any proceeding for debarment is pending or, to the best of the investigator's knowledge, threatened.

In the event the Sponsor prematurely terminates a particular trial site, the Sponsor will promptly notify that trial site's IRB/IEC.

According to European legislation, a Sponsor must designate an overall coordinating investigator for a multi-center trial (including multinational). When more than one trial site is open in an EU country, Merck, as the Sponsor, will designate, per country, a national principal coordinator (Protocol CI), responsible for coordinating the work of the principal investigators at the different trial sites in that Member State, according to national regulations. For a single-center trial, the Protocol CI is the principal investigator. In addition, the Sponsor must designate a principal or coordinating investigator to review the trial report that summarizes the trial results and confirm that, to the best of his/her knowledge, the report accurately describes the conduct and results of the trial [Clinical Study Report (CSR) CI]. The Sponsor may consider one or more factors in the selection of the individual to serve as the Protocol CI and or CSR CI (e.g., availability of the CI during the anticipated review process, thorough understanding of clinical trial methods, appropriate enrollment of subject cohort, timely achievement of trial milestones). The Protocol CI must be a participating trial investigator.

